Academic and Community Cancer Research United (ACCRU)

A Multicenter Phase II Study of Pembrolizumab (MK-3475) in Patients with Advanced Small Bowel Adenocarcinomas

*For any communications regarding this protocol,
please contact the person listed on the Protocol Resource page. This is a stand-alone document found on
the ACCRU website (www.ACCRU.org).*

Study Chairs

[figure not shown]
ACCRU: [name].
Mayo Clinic
[name]
[contact]

FDA IND Sponsor/Investigator: [name].

Study Co-chairs:

Statistician:

 Mayo Clinic

Drug Availability

Drug Company Supplied: Pembrolizumab (MK-3475) Commercial supply provided by Merck) IND #130955

✓ Study contributor(s) not responsible for patient care.

NCI: NCT02949219
Merck MISP# 52192

Research Coordinating Center
Academic and Community Cancer Research United
[name]
[name]
[contact]

Document HistoryEffective Date

[figure not shown]
[figure not shown]
Pre-activation ACCRU	September 30, 2016
Activation Addendum 1	February 24, 2017
Addendum 2	September 15, 2017
Addendum 3	April 27, 2018
Addendum 4	September 06, 2019
Addendum 5	September 27, 2019

Index

Schema

- 1.0 Background
- 2.0 Goals
- 3.0 Patient Eligibility
- 4.0 Test Schedule
- 5.0 Stratification Factors
- 6.0 Registration Procedures
- 7.0 Protocol Treatment
- 8.0 Dosage Modification Based on Adverse Events
- 9.0 Ancillary Treatment/Supportive Care
- 10.0 Adverse Event (AE) Reporting and Monitoring
- 11.0 Treatment Evaluation Using RECIST Guideline
- 12.0 Descriptive Factors
- 13.0 Treatment/Follow-up Decision at Evaluation of Patient
- 14.0 Body Fluid Biospecimens
- 15.0 Drug Information
- 16.0 Statistical Considerations and Methodology
- 17.0 Pathology Considerations/Tissue Biospecimens
- 18.0 Records and Data Collection Procedures
- 19.0 Budget
- 20.0 References

Schema

Primary outcome is response based on RECIST criteria. Secondary endpoints are PFS, OS, and adverse events.

*To permit continued study treatment beyond initial radiographic disease progression, see section 7.6 Treatment Continuation.

Cycle length = 21 days

Generic name: Pembrolizumab

Brand name(s): Keytruda

ACCRU Abbreviation:

Availability: Clinical Research Services, a division of Rx Crossroads by McKesson

1.0 Background

Trial Summary

Abbreviated Title	Pembrolizumab in advanced small bowel adenocarcinoma
Trial Phase	Phase II
Clinical Indication	Treatment of subjects with advanced small bowel adenocarcinoma after first-line treatment
Trial Type	Interventional
Type of control	None
Route of administration	Intravenous
Trial Blinding	Unblinded, open-label
Treatment Groups	All patients receive pembrolizumab 200 mg every 3 weeks.
Number of trial subjects	41 patients
Estimated enrollment period	The sponsor estimates that the trial will require approximately 17 months from the first patient enrolling until the final patient signs informed consent.
Estimated duration of trial	The sponsor estimates that the trial will require approximately 20 months to allow full accrual and at least the first 4 cycles of pembrolizumab.
Duration of Participation	Until disease progression, drug intolerance, or 24 months of pembrolizumab therapy.

1.1 Pharmaceutical and Therapeutic Background

The importance of intact immune surveillance in controlling outgrowth of neoplastic transformation has been known for decades. Accumulating evidence shows a correlation between tumor-infiltrating lymphocytes (TILs) in cancer tissue and favorable prognosis in various malignancies. In particular, the presence of CD8+ T-cells and the ratio of CD8+ effector T-cells / FoxP3+ regulatory T-cells seems to correlate with improved prognosis and long-term survival in many solid tumors.

The PD-1 receptor-ligand interaction is a major pathway hijacked by tumors to suppress immune control. The normal function of PD-1, expressed on the cell surface of activated T-cells under healthy conditions, is to down-modulate unwanted or excessive immune responses, including autoimmune reactions. PD-1 (encoded by the gene *Pdcd1*) is an Ig superfamily member related to CD28 and CTLA-4 which has been shown to negatively regulate antigen receptor signaling upon engagement of its ligands (PD-L1 and/or PD-L2). The structure of murine PD-1 has been resolved. PD-1 and family members are type I transmembrane glycoproteins containing an Ig Variable-type (V-type) domain responsible for ligand binding and a cytoplasmic tail which is responsible for the binding of signaling molecules. The cytoplasmic tail of PD-1 contains 2 tyrosine-based signaling motifs, an immunoreceptor tyrosine-based inhibition motif (ITIM) and an immunoreceptor tyrosine-based switch motif (ITSM). Following T-cell stimulation, PD-1 recruits the tyrosine phosphatases SHP-1 and SHP-2 to the ITSM motif within its cytoplasmic tail, leading to the dephosphorylation of effector molecules such as CD3 ζ , PKC θ and ZAP70 which are involved in the CD3 T-cell signaling cascade. The mechanism by which PD-1 down modulates T-cell responses is similar to, but distinct from that of CTLA-4 as both molecules regulate an overlapping set of signaling proteins. PD-1 was shown to be expressed on activated lymphocytes including peripheral CD4+

and CD8+ T-cells, B-cells, Tregs and Natural Killer cells. Expression has also been shown during thymic development on CD4-CD8- (double negative) T-cells as well as subsets of macrophages and dendritic cells. The ligands for PD-1 (PD-L1 and PD-L2) are constitutively expressed or can be induced in a variety of cell types, including non-hematopoietic tissues as well as in various tumors. Both ligands are type I transmembrane receptors containing both IgV- and IgC-like domains in the extracellular region and contain short cytoplasmic regions with no known signaling motifs. Binding of either PD-1 ligand to PD-1 inhibits T-cell activation triggered through the T-cell receptor. PD-L1 is expressed at low levels on various non-hematopoietic tissues, most notably on vascular endothelium, whereas PD-L2 protein is only detectably expressed on antigen-presenting cells found in lymphoid tissue or chronic inflammatory environments. PD-L2 is thought to control immune T-cell activation in lymphoid organs, whereas PD-L1 serves to dampen unwarranted T-cell function in peripheral tissues. Although healthy organs express little (if any) PD-L1, a variety of cancers were demonstrated to express abundant levels of this T-cell inhibitor. PD-1 has been suggested to regulate tumor-specific T-cell expansion in subjects with melanoma (MEL). This suggests that the PD-1/PD-L1 pathway plays a critical role in tumor immune evasion and should be considered as an attractive target for therapeutic intervention.

Pembrolizumab is a potent and highly selective humanized monoclonal antibody (mAb) of the IgG4/kappa isotype designed to directly block the interaction between PD-1 and its ligands, PD-L1 and PD-L2. Keytruda™ (pembrolizumab) has recently been approved in the United States for the treatment of patients with unresectable or metastatic melanoma and disease progression following ipilimumab and, if BRAF V600 mutation positive, a BRAF inhibitor.

1.2 Preclinical and Clinical Trial Data

Refer to the Investigator's Brochure for Preclinical and Clinical data.

[figure not shown]
Small bowel adenocarcinoma (SBA) is a rare malignancy that is often diagnosed in its late stages. Due to its rarity, it is historically understudied. As such, there is no clear, consistent standard of care. This is further complicated by a noted heterogeneous response to standard chemotherapy regimens. To date, small prospective clinical studies have evaluated chemotherapy for SBA the first of which examined the use of mitomycin C, Adriamycin, and 5-fluorouracil with minimal therapeutic effect. (Gibson, Holcroft et al. 2005). This study was performed in the early 1980s but not reported until 2005.

More recently oxaliplatin-based therapies have been demonstrated to have activity and have emerged as a standard of care in the front line setting. Overman et al. demonstrated a high response rate (50%) with combination therapy of oxaliplatin and capecitabine although the trial also included patients with ampullary carcinoma. (Overman, Varadhachary et al. 2009) This study showed that small bowel carcinoma is a chemosensitive disease with response rates and sensitivity profile similar to other GI malignancies, namely fluoropyrimidine and oxaliplatin-based therapy. A Chinese study using FOLFOX showed similar response rates, progression free survival, and overall survival to the XELOX study (Table 1). (Xiang, Liu et al. 2012) A recently completed multicenter trial, N0543 is a small bowel adenocarcinoma study using a triplet combination of irinotecan, oxaliplatin, and capecitabine, with UGT1A1 genotype-based therapy. This study has demonstrated the feasibility of performing a small adenocarcinoma study within a cooperative group, in this case the North Central Cancer Treatment Group, now part of the Alliance for Clinical Trials in Oncology. (McWilliams, Mahoney et al. 2012) While oxaliplatin-based therapy is widely considered the standard for first line therapy, there is no clearly established therapy beyond first line treatment for SBA, as no prospective trials have been performed to date.

Table 1. Prospective Trials for Oxaliplatin-based therapy in Metastatic SBA

Study	Regimen	# patients	PFS (mo.)	OS (mo.)	RR (%)
Overman et al. (2009)	XELOX	30	9.4	15.5	50
McWilliams et al (2012)	XELIRINOX	29	8.7	13.2	39
Xiang (2012)	FOLFOX	33	7.8	15.2	48

Similar to patterns seen in colorectal cancer (Gonsalves, Mahoney et al. 2014; Missiaglia, Jacobs et al. 2014), there appears to be genetic heterogeneity among sites of small bowel adenocarcinoma primary tumor origination. This may correspond with differences in overall survival, as we have noted in examining outcomes of 50 small bowel patients seen at the Mayo Clinic (**Figure 1**). (Unpublished data) For instance, tumors deficient in DNA mismatch repair and having resulting high microsatellite instability (dMMR/MSI-H) appear more often in proximal tumors, and KRAS mutations are more common in duodenal cancers (57% vs. jejunum (29%) and ileum (14%)).(Aparicio, Svrcek et al. 2013) Her-2 expression levels appear to be lowest in proximal tumors and highest in ileal tumors. While several of these genetic mutations that have been noted in small bowel adenocarcinomas are potentially targetable with therapy, the frequency is too low, even when attempting screening by the above known tumor site characteristics, in this rare cancer to allow for feasible clinical study.

[figure not shown]
Figure 1. Survival by primary tumor site

1.3 Rationale for the Trial and Selected Subject Population

Beyond conventional chemotherapy for these tumors, there are no known SBA-specific genetic targets that have been investigated for treatment efficacy. Genetic analyses have revealed similar molecular characteristics to colorectal cancer. Recently, a European coalition investigated 46 commonly altered cancer genes in 83 cases and found that the most common mutations are not therapeutically targeted: KRAS, TP53, APC, and smad4 (Laforest, Aparicio et al. 2014). There may be a population of Her2, BRAF, or PI3KCA patients who may benefit from signaling pathway blockade, but with the rarity of those mutations ($\leq 15.8\%$) in a rare disease, trials will be difficult to accrue. There is an urgent need to perform larger, coordinated international studies to establish further evidence-based therapeutic options.

The relative rarity of adenocarcinoma of the small bowel compared to the colon or stomach is postulated to be related to increased immune surveillance in the small intestine (Lowenfels 1973) suggesting that, in those tumors that do develop in the small bowel, immune checkpoint therapies may be widely useful in re-establishing anti-tumor immune function.

We performed a pilot study of PD-L1 staining of 50 archived small bowel adenocarcinoma tumors. In this study, 4 patients (8%) had strong cellular staining for PD-L1, while 21/50 (42%) had 3+ or greater staining of intratumoral stroma. In an unadjusted survival analysis, tumors that showed cellular staining for PD-L1 were associated with a poorer survival (median survival 10 months vs 5.5 years, $p = 0.0009$ by Log-Rank), though the cohort size was too small to draw general conclusions (Figure 2). There was no difference in outcome by stromal staining 3+/4+ vs 0, 1+, 2+ ($p=0.51$). The poor survival of PD-L1 staining tumors is similar to what is reported for renal cell carcinoma, suggesting impaired immune surveillance and providing the rationale for PD1 targeted therapy in this disease. (Thompson, Gillett et al. 2004).

Figure 2. Survival by tumor cell staining for PD-L1

It has recently been suggested that dMMR/MSI-H patients may have a superior response to anti-PD1 therapy. (Le, Uram et al. 2015) In our preclinical study, seven of the 50 tumors (14%) were already known clinically to be dMMR/MSI-H. These had a superior prognosis to tumors not known to be dMMR/MSI-H (median survival not reached vs 2.5 years, $p=0.028$ by Log-Rank), suggesting a unique biology at baseline and is in keeping with survival data on Lynch syndrome patients with cancer of the large intestine. While the response to PD-1 inhibitors was most prominent in the dMMR cohort of the Le et al. study (ORR 40%), a small number of patients with proficient MMR and microsatellite stability (pMMR/MSS) did achieve a small response or stable disease, indicating potential efficacy in both cohorts.

Our goal is to evaluate whether pembrolizumab administered to patients with advanced small bowel adenocarcinoma in second- or later lines of therapy demonstrates antitumor activity as measured by confirmed response rate. Secondary endpoints would include response in dMMR vs. pMMR patients, response in PD-L1 (+) vs. PD-L1 (-) expressers, progression-free survival (PFS), overall survival (OS), and tolerability.

1.4 Rationale for Dose Selection/Regimen/Modification

An open-label Phase I trial (Protocol 001) is being conducted to evaluate the safety and clinical activity of single agent MK-3475. The dose escalation portion of this trial evaluated three dose levels, 1 mg/kg, 3 mg/kg, and 10 mg/kg, administered every 2 weeks (Q2W) in subjects with advanced solid tumors. All three dose levels were well tolerated and no dose-limiting toxicities were observed. This first in human study of MK-3475 showed evidence of target engagement and objective evidence of tumor size reduction at all dose levels (1 mg/kg, 3 mg/kg and 10 mg/kg Q2W). No MTD has been identified to date. Recent data from other clinical studies within the MK-3475 program has shown that a lower dose of MK-3475 and a less frequent schedule may be sufficient for target engagement and clinical activity(Daud, Ribas et al. 2015).

PK data analysis of MK-3475 administered Q2W and Q3W showed slow systemic clearance, limited volume of distribution, and a long half-life (refer to IB).

Pharmacodynamic data (IL-2 release assay) suggested that peripheral target engagement is durable (>21 days). This early PK and pharmacodynamic data provides scientific rationale for testing a Q2W and Q3W dosing schedule.

A population pharmacokinetic analysis has been performed using serum concentration time data from 476 patients. Within the resulting population PK model, clearance and volume parameters of MK-3475 were found to be dependent on body weight. The

relationship between clearance and body weight, with an allometric exponent of 0.59, is within the range observed for other antibodies and would support both body weight normalized dosing or a fixed dose across all body weights. MK-3475 has been found to have a wide therapeutic range based on the melanoma indication. The differences in exposure for a 200 mg fixed dose regimen relative to a 2 mg/kg Q3W body weight based regimen are anticipated to remain well within the established exposure margins of 0.5 – 5.0 for MK-3475 in the melanoma indication. The exposure margins are based on the notion of similar efficacy and safety in melanoma at 10 mg/kg Q3W vs. the proposed dose regimen of 2 mg/kg Q3W (i.e. 5-fold higher dose and exposure). The population PK evaluation revealed that there was no significant impact of tumor burden on exposure. In addition, exposure was similar between the NSCLC and melanoma indications. Therefore, there are no anticipated changes in exposure between different indication settings.

The rationale for further exploration of 2 mg/kg and comparable doses of pembrolizumab in solid tumors is based on: 1) similar efficacy and safety of pembrolizumab when dosed at either 2 mg/kg or 10 mg/kg Q3W in melanoma patients, 2) the flat exposure-response relationships of pembrolizumab for both efficacy and safety in the dose ranges of 2 mg/kg Q3W to 10 mg/kg Q3W, 3) the lack of effect of tumor burden or indication on distribution behavior of pembrolizumab (as assessed by the population PK model) and 4) the assumption that the dynamics of pembrolizumab target engagement will not vary meaningfully with tumor type.

The choice of the 200 mg Q3W as an appropriate dose for the switch to fixed dosing is based on simulations performed using the population PK model of pembrolizumab showing that the fixed dose of 200 mg every 3 weeks will provide exposures that 1) are optimally consistent with those obtained with the 2 mg/kg dose every 3 weeks, 2) will maintain individual patient exposures in the exposure range established in melanoma as associated with maximal efficacy response and 3) will maintain individual patients exposure in the exposure range established in melanoma that are well tolerated and safe. A fixed dose regimen will simplify the dosing regimen to be more convenient for physicians and to reduce potential for dosing errors. A fixed dosing scheme will also reduce complexity in the logistical chain at treatment facilities and reduce waste.

2.0 Goals

2.1 Primary Objective and Endpoint

- 2.11 To determine whether pembrolizumab administered to SBA patients demonstrates antitumor activity as measured by the confirmed response rate

2.2 Secondary Objectives and Endpoints

- 2.21 To assess survival endpoints (OS, PFS), including stratified analysis by tumor site.
- 2.22 To assess whether pembrolizumab is safe in SBA patients by assessing adverse events.

2.3 Correlative Research

- 2.31 To determine whether PD-L1 expression, as measured by IHC, or MSI status is associated with the response rate overall.
- 2.32 To determine if Bim levels in tumor-reactive CD11ahighPD-1+CD8+ peripheral

blood T cells can objectively monitor responses to pembrolizumab and to determine if excessive release of soluble B7-H1 (sPD-L1) by the tumor leads to Bim upregulation and treatment resistance in SBA.

2.33 To determine if other tissue-based factors, such as total mutational burden, correlate with response to pembrolizumab.

3.0 Patient Eligibility

3.1 Inclusion Criteria

3.11 Patients must have biopsy-proven adenocarcinoma of the small bowel at any site (duodenum, jejunum, ileum), excluding ampullary and appendiceal tumors.

3.12 Have locally advanced (unresectable) or metastatic small bowel adenocarcinoma.

3.13 Willing and able to provide written informed consent for the trial.

3.14 Age \geq 18 years.

3.15 Measurable disease based on RECIST 1.1.

3.16 Had at least one prior line of systemic chemotherapy for metastatic disease. Adjuvant therapy would not count toward first-line therapy unless patient recurs less than 6 months after completion of that regimen.

3.17 Willing to provide blood and tissue (can be archival) samples for mandatory research purposes (see sections 4.0, 14.0 and 17.0).

3.18 ECOG Performance Status (PS) 0 or 1. (Form is available on the ACCRU web site)

3.19a The following laboratory values obtained \leq 28 days prior to registration.

- Absolute neutrophil count (ANC) \geq 1500/mm³ ($1.50 \times 10^9/L$)
- Platelet count \geq 100,000/mm³ ($100 \times 10^9/L$)
- Hemoglobin \geq 9.0 g/dL (5.6 mmol/L or 90 g/L) without transfusion or EPO dependency (within 7 days of assessment)
- Serum total bilirubin \leq 1.5x upper limit of normal (ULN) **OR** direct bilirubin \leq ULN for subjects with total bilirubin levels $>$ 1.5x ULN
- Aspartate transaminase (AST) and alanine aminotransferase (ALT) \leq 2.5x ULN **OR** \leq 5x ULN for subjects with liver metastases
- Serum creatinine \leq 1.5x upper limit of normal (ULN)
OR
- Measured or calculated creatinine clearance must be \geq 60 mL/min for subjects with creatinine levels $>$ 1.5 X ULN using the Cockcroft-Gault formula below (Glomerular Filtration Rate [GFR] \geq 60 mL/min (1.0 mL/s/m²) can also be used in place of creatinine or CrCl):

Cockcroft-Gault Equation:

$$\text{Creatinine clearance for males} = \frac{(140 - \text{age})(\text{weight in kg})}{(72)(\text{serum creatinine in mg/dL})}$$

$$\text{Creatinine clearance for females} = \frac{(140 - \text{age})(\text{weight in kg})(0.85)}{(72)(\text{serum creatinine in mg/dL})}$$

3.19b Female subject of childbearing potential have a negative urine or serum pregnancy ≤ 7 days prior to registration. If the urine test is positive or cannot be confirmed as negative, a serum pregnancy test will be required.
 Note: Female subjects of childbearing potential should be willing to use 2 methods of birth control or be surgically sterile, or abstain from heterosexual activity for the course of the study through 120 days after the last dose of study medication. Subjects of childbearing potential are those who have not been surgically sterilized or have not been free from menses for > 1 year. Male subjects should agree to use an adequate method of contraception starting with the first dose of study therapy through 120 days after the last dose of study therapy.

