4.0 Test Schedule

Tests and procedures	Active Monitoring Phase			
	≤28 days prior to registration	Day 1 Cycle 1	Day 1 Cycles 2 -8 and beyond (+/-3 days)	End of treatment (PD, withdrawal, or removal ⁹) (+7days)
History and exam, wt, ECOG PS	X	X ^{6,8}	X ⁶	X
Height	X			
Adverse event assessment	X	X ⁸	X	X
Concomitant medication review	X	X ⁸	X	
Hematology: CBC/ differential	X	X	X	X
Chemistry: SGOT (AST), ALT, alk phos, T. bili, creatinine, calcium,, Na, K, glucose, LDH, bicarbonate, uric acid, Mg, Phosphorus, total protein, blood urea nitrogen, albumin	X	X	X	
PT/INR and aPTT	X			
Urinalysis ³	X			
T3, FT4 and TSH	X	X	X	
Tumor measurement (should include at least a CT of the abdomen/pelvis, and appropriate imaging of any other target site lesions) ^{1, 10}	X		X ⁵	X
CEA	X		X ⁷	X
Pregnancy test	X ²			
Mandatory blood sample (see Section 14.0) ⁸	X	X	X ⁴	X
Mandatory tissue sample (see Section 17.0)	X			

1. Use same imaging throughout the study.
2. For women of childbearing potential only. Must be done ≤7 days prior to registration.
3. Urine blood, glucose, protein, specific gravity. Microscopic exam if abnormalities on urinalysis results.
4. Collected cycles 2, 3, 4, 8 (see Section 14.0). Kits are required for this collection.
5. Every 4 cycles beginning with end of cycle 4, and at end of treatment.
6. Directed physical exam only.
7. Every even-numbered cycle, beginning with cycle 2, and at end of treatment.
8. ≤24 hours prior to treatment.
9. Continued study treatment beyond initial radiographic disease progression may be allowed; see Section 13.4 for details. These

patients would continue follow-up per test schedule until confirmed progression.

10. To be submitted <60 days after registration

R Research funded (see Section 19.0). Mandatory research blood draws should be collected and submitted *after* the patient is registered onto the study, but before beginning study treatment.

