6.3 Documentation of IRB approval

Documentation of IRB approval must be on file in the Registration Office before an investigator may register any patients. Approvals should be uploaded using the online ACCRU Regulatory Management System (ARMS).

In addition to submitting initial IRB approval documents, ongoing IRB approval documentation must be on file (no less than annually) with ACCRU. Approvals should be uploaded using the online [REDACTED]. If the necessary documentation is not submitted in advance of attempting patient registration, the registration will not be accepted and the patient may not be enrolled in the protocol until the situation is resolved.

Submission of annual IRB approvals is required until the study has been closed through your IRB.

6.4 Prior to accepting the registration, the registration/randomization, the registration/randomization application will verify the following:

- IRB approval at the registering institution
- Patient eligibility

- Existence of a signed consent form
- Existence of a signed authorization for use and disclosure of protected health information

6.5 At the time of registration, the following will be recorded:

- Patient has/not given permission to store and use his/her sample(s) for future research to learn about, prevent, or treat cancer.
- Patient has/not given permission to store and use his/her sample(s) for future research to learn, prevent, or treat other health problems (for example: diabetes, Alzheimer's disease, or heart disease).
- Patient has/not given permission for ACCRU to give his/her sample(s) to outside researchers.

6.6 Treatment cannot begin prior to registration and must begin ≤ 10 days after registration.

6.7 Pretreatment tests/procedures (see Section 4.0) must be completed within the guidelines specified on the test schedule.

6.8 All required baseline symptoms (see Section 10.5) must be documented and graded.

6.9a Treatment on this protocol must commence at an ACCRU institution under the supervision of a medical oncologist.

6.9b Study drug is available on site.

6.9c Blood draw kit is available on site.

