7.0 Protocol Treatment

7.1 Treatment Schedule

Drug	Dose/Potency	Dose Frequency	Route of Administration	Regimen/Treatment Period	Use
Pembrolizumab	200 mg (flat dosing)	Q3W	IV infusion	Day 1 of each 3 week cycle	Experimental

Note: Trial treatment should begin ≤ 10 days after registration and as close as possible to the date on which treatment is allocated/assigned.

Note: Details on preparation and administration of pembrolizumab (MK-3475) are provided in section 15.0.

7.2 For this protocol, the patient must return to the consenting ACCRU institution for evaluation at least every 21 days (+/- 3 days) during treatment.

7.3 Dosing interruptions, not due to adverse effects.

Dosing interruptions are permitted in the case of medical / surgical events or logistical reasons not related to study therapy (e.g., elective surgery, unrelated medical events, patient vacation, and/or holidays). Subjects should be placed back on study therapy within 3 weeks of the scheduled interruption. The reason for interruption should be documented in the patient's study record.

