7.4 Timing of Dose Administration

Trial treatment should be administered on Day 1 of each cycle after all procedures/assessments have been completed. Trial treatment may be administered up to 3 days before or after the scheduled Day 1 of each cycle due to administrative reasons.

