7.82 Contraception

Pembrolizumab may have adverse effects on a fetus in utero. Furthermore, it is not known if pembrolizumab has transient adverse effects on the composition of sperm. Non-pregnant, non-breast-feeding women may be enrolled if they are willing to use 2 methods of birth control or are considered highly unlikely to conceive. Highly unlikely to conceive is defined as 1) surgically sterilized, or 2) postmenopausal (a woman who is ≥ 45 years of age and has not had menses for greater than 1 year will be considered postmenopausal), or 3) not heterosexually active for the duration of the study. The two birth control methods can be either two barrier methods, or a barrier method plus a hormonal method to prevent pregnancy. Subjects should start using birth control from study Visit 1 throughout the study period up to 120 days after the last dose of study therapy. The following are considered adequate barrier methods of contraception: diaphragm, condom (by the partner), copper intrauterine device, sponge, or spermicide. Appropriate hormonal contraceptives will include any registered and marketed contraceptive agent that contains an estrogen and/or a progestational agent (including oral, subcutaneous, intrauterine, or intramuscular agents).

Subjects should be informed that taking the study medication may involve unknown risks to the fetus (unborn baby) if pregnancy were to occur during the study. In order to participate in the study they must adhere to the contraception requirement (described above) for the duration of the study and during the follow-up period. If there is any question that a subject will not reliably comply with the requirements for contraception, that subject should not be entered into the study.

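### The only first-course pregnancy test is timed to registration, so a compliant test can be up to 17 days old at the first dose, and no pregnancy test is scheduled at Cycle 1 Day 1

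*Combined protocol and SAP*

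**What the plan says.** Two places time the first-course pregnancy test, and they agree. Section 3.19b sets the eligibility condition: "Female subject of childbearing potential have a negative urine or serum pregnancy ≤ 7 days prior to registration". It adds a serum test when the urine result is positive or cannot be read as negative. Footnote 2 to the Section 4.0 test schedule says of the same test: "Must be done ≤7 days prior to registration". In that schedule the pregnancy row is marked only in the pre-registration column.

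Two places limit the time from registration to first dose. Section 6.6: "Treatment cannot begin prior to registration and must begin ≤ 10 days after registration". The note in Section 7.1 repeats the limit and asks for promptness: "Trial treatment should begin ≤ 10 days after registration and as close as possible to the date on which treatment is allocated/assigned".

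On the reason for testing, Section 7.82 states: "Pembrolizumab may have adverse effects on a fetus in utero". Section 3.29i excludes women who are pregnant or expecting to conceive. On prevention, the note to Section 3.19b begins: "Female subjects of childbearing potential should be willing to use 2 methods of birth control", with sterility or abstinence as alternatives. Section 7.82 adds: "Subjects should start using birth control from study Visit 1 throughout the study period", and bars entry where reliable compliance is in question.

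The one test timed to dosing is in Section 13.9, which asks for a negative result no more than 72 hours before second-course retreatment.

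**The concern.** The test is tied to registration, but fetal exposure begins at the first infusion. Up to 10 further days can pass between the two, and nothing in the schedule brings the test up to date. A pregnancy too early to show at screening, or one beginning after the test, could go undetected when the first dose is given.

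The later safeguards act after exposure. Sections 7.83 and 13.5 remove a participant once pregnancy is known, but they schedule no test that would reveal it. Removal also does not end exposure at once: Section 15.15 gives a terminal half-life of 22 days, and contraception is required for 120 days after the last dose.

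What is at stake is the safety of a small, unstated number of participants and any fetus. No statistical property of the trial depends on it.

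**Working it through.** The plan states no figure for test age at first dose, so there is none to reproduce. The check adds the two permitted windows.

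**Inputs**
- *a*, days from test to registration: 0 to 7 (Section 3.19b; Section 4.0 footnote 2).
- *d*, days from registration to first dose: 0 to 10 (Sections 6.6 and 7.1).
- Comparison window: 72 hours = 3 days (Section 13.9, retreatment only).

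**Test age at first dose = *a* + *d***
- Latest permitted start, *d* = 10: maximum 7 + 10 = **17 days**.
- Same-day start, *d* = 0: maximum 7 + 0 = **7 days**.
- For start days 0 to 10 the maximum rises by one day per day, from 7 to 17. The minimum is 0 + 0 = 0 days.

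**With a 72-hour limit before the first dose**
- Maximum age is 3 days: 17 − 3 = 14 days less for the latest start, and 7 − 3 = 4 days less for a same-day start.

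**When one test can serve both rules**
- This needs *a* + *d* ≤ 3, which is possible only for starts on days 0 to 3. A same-day start allows *a* up to 3; a day-3 start needs *a* = 0.
- For starts on days 4 to 10, any test taken by registration is already more than 72 hours old, so a repeat is always needed.

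**Fit with the 10-day start limit**
- For a day-10 start, the repeat can be taken from day 10 − 3 = 7, leaving up to 3 days for a serum result.
- If dosing slips, a further repeat may be needed. Example: start planned for day 5, repeat taken on day 2, dosing moved to day 9. The repeat is then 9 − 2 = 7 days old and must be done again.

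**How many women**
- Section 16.9d plans for 13 women among 41 patients. That counts women of all ages, is a planning figure and is not a cap. The number of childbearing potential is not given.
- The documents give no detection limits for the tests, so the number of missed pregnancies avoided cannot be calculated.

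**The case against.** The strongest reply is that this is a preference and not an error. The eligibility text and the schedule agree with each other, the two start limits agree, and no rule in the documents requires a test timed to the first dose. That stands. A reader might infer a contradiction between Section 3.19b and Section 13.9, but the documents do not support one: the first is an entry check, the second a condition for restarting after treatment has stopped. The 72-hour rule is also a modest precedent. Its contraception bullet refers to a Section 5.7.2 that this protocol does not contain, which suggests carried-over text. It shows that a dose-timed test is workable here, not that the protocol set 72 hours as its standard for first dosing.

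A reader might also infer that nothing is checked at the first dose. That is wrong. Section 4.0 schedules a history and directed exam, an adverse event assessment and a medication review at Cycle 1 Day 1, and footnote 8 places them no more than 24 hours before treatment. Only a pregnancy test is absent.

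Nor should 17 days be read as typical. It needs both windows at their limits, and Section 7.1 asks for a prompt start. The contraception rules and Section 3.29i lower the risk further, although Section 7.82 counts contraception from a Visit 1 that Section 4.0 does not define.

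Finally, one added test leaves later first-course doses without a scheduled pregnancy test, and a test up to 72 hours old can still miss an early pregnancy. Both limits are real. They bound what the change achieves but do not remove the reason for it.

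**Conclusion.** The gap is real and minor. A participant can meet every rule and receive her first infusion on a pregnancy test 17 days old, or 7 days old with a same-day start. The existing safeguards reduce the chance of harm, but none of them updates the test. This is best treated as a cheap improvement in participant safety, not as a defect in the trial's logic.

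The two maxima rest only on the stated windows, counted in whole days, and are certain as permitted limits. How often the long interval would occur, and how many pregnancies a later test would find, cannot be known from the documents. A reader might conclude that pregnant women are likely to be treated; nothing in the documents supports a statement of likelihood either way. The primary endpoint, sample size and analysis are not affected.

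**What to change.** Keep the eligibility test as it is. Add to Section 3.19b and to footnote 2 of Section 4.0:

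> For women of childbearing potential, if the most recent negative test is more than 72 hours old at the first dose, repeat a urine pregnancy test within 72 hours before the first dose, normally at the Cycle 1 Day 1 visit. If it is positive or cannot be confirmed as negative, a negative serum test is required before dosing.

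Mark the test in the Cycle 1 Day 1 column of Section 4.0. Section 7.4 then makes it a check before dosing without further change: "Trial treatment should be administered on Day 1 of each cycle after all procedures/assessments have been completed". State also that a registered woman confirmed pregnant before dosing is not treated and is handled as a cancel under Section 13.3.

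**Cost.** One short addition in two places, one mark in the table and a line on handling. For the women concerned it usually means one repeat urine test at a visit that already takes place. Occasionally a serum test is needed, and its result must return within the 10-day start limit; for a start near day 10 the repeat should be taken early in its window, which may mean a separate sample. A further repeat is needed if dosing slips more than 72 hours after the first repeat. The change covers the first dose only.
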